7.6 Safety Assessments

7.6.1 Gynecological Examination

The Investigator will perform a gynecological examination as per the usual clinical practice. Information about all gynecological examinations must be included in the source documentation at the study site and be signed and dated by the Investigator or designee. Only new, abnormal findings in the gynecological examination should be

captured in the eCRF. Significant changes should be assessed by the Investigator or Sub-investigator and considered for potential reporting as an AE. Date of examination will be entered in the eCRF.

Subjects with uterine or vaginal prolapse of \geq Grade 2 or higher at screening should not be included in the study. The recommended grading to be used for evaluation at screening can be found in Appendix 8.

7.6.2 Breast Examination

A standard breast examination should be conducted by the Investigator. Information about all breast examinations must be included in the source documentation at the study site and be signed and dated by the Investigator or designee. Only new, abnormal findings in the breast examination should be captured in the eCRF. Significant changes should be assessed by the Investigator and considered for potential reporting as an AE. The date of examination will be entered in the eCRF.

7.6.3 Cervical Cytology (Papanicolaou) Smear

Cervical smear samples will be analyzed by Cytotechnologists and a pathologist at the central pathology laboratory and will be classified according to the Bethesda 2001 System. Date of specimen collection will be entered in the eCRF. Subjects with the following classifications at Visit 1 are not eligible for the study:

- Atypical Squamous Cells of Undetermined Significance (ASCUS) (human papilloma virus [HPV] High Risk Positive),
- Atypical Squamous Cells - cannot exclude high-grade squamous intraepithelial lesion (HSIL),
- Atypical Glandular Cells (Endocervical, Endometrial, not otherwise specified [NOS]),
- Low Grade squamous intraepithelial lesion (SIL),
- High Grade SIL,
- Carcinoma, and
- Unsatisfactory specimen (one retest will be allowed).

Detailed procedures for sample collection, handling, labeling, storage, and shipping will be specified in a separate document. Details about the central pathology laboratory are provided in Section 10.1.

7.6.4 Transvaginal Ultrasound (for Subjects with an Intact Uterus Only)

A transvaginal ultrasound (TVU) will be conducted to assess the uterus and adnexa. Images obtained will also be used to determine endometrial thickness at the central ultrasound laboratory. Date of the TVU will be entered in the eCRF. The TVU must be performed by a trained study staff member and images must be sent to a central reader. The results of the TVU at Visit 1 (Screening), including centrally-determined endometrial

thickness, will be used to assess eligibility. The subject should not be randomized until the centrally read TVU result indicates the endometrial thickness (double-layer) is <4 mm.

If at Screening, the locally read endometrial thickness is evidently, according to the Investigators judgment, more than 4 mm, the subject would not be eligible for the study and the images from the TVU should not be sent to the central ultrasound laboratory.

At 12 weeks (Visit 5), the TVU will be performed and the endometrial thickness (double-layer) will be determined by a central reader following the same procedure. If the subject leaves the study before Week 12, the TVU should be performed as part of the early termination visit.

Any symptomatic and/or large fibroids (estimated size >3 cm) or uterine polyps observed in the TVU at Screening (Visit 1) will exclude the subject from the study. Subjects with endometrial polyps identified during the study period will be discontinued, endometrial polyps should be reported as an AE, and the AE should be captured as the reason for discontinuation.

Detailed procedures will be specified in a separate document. Details about the central ultrasound laboratory are provided in Section 10.1.

7.6.5 Biopsy for Endometrial Histology (for Subjects with Intact Uterus Only)

The endometrial biopsy must be obtained after the TVU is performed. Use of oral pain medication is allowed before the biopsy. Local anesthesia will be used if considered necessary by the Investigator. The use of any concomitant medication must be recorded in the eCRF. Endometrial biopsy samples will be taken by the Investigator using a suction curette (Pipelle® or equivalent, aspiration technique). All endometrial samples will be shipped to the central pathology laboratory for preparation of slides.

The endometrial biopsy performed at Visit 1 will be used to evaluate the subject's eligibility for the study and to establish a baseline reading. Subjects with normal or atrophic endometrial histology are eligible to be randomized. Subjects with an insufficient biopsy sample after a valid attempt will be eligible for the study, if the endometrial thickness is <4 mm in the centrally-read TVU. If an endometrial sample cannot be obtained due to cervical stenosis (ie, cervical os cannot be penetrated), the subject is not eligible for the study.

All endometrial histological samples (slides) will be analyzed by concurrent readings by three independent pathologists. Each pathologist will be blinded to the treatment group and to the readings of the other pathologists. The concurrence of two of the three pathologists will be the final diagnosis. If there is no agreement among the three pathologists, the most severe pathologic diagnosis would be used as the final diagnosis. All pathologists will be blinded both to the study treatment and to each other's readings of the histology slides.

Assessment of biopsies will be made according to predefined and generally accepted microscopic criteria (Blaustein's classification). Subjects found to have endometrial hyperplasia or endometrial cancer at screening will be excluded from the study. Subjects found to have endometrial hyperplasia or endometrial cancer during the study will be discontinued and endometrial hyperplasia or endometrial cancer should be reported as an AE, and the AE should be captured as the reason for discontinuation. The subject will be referred for standard of care clinical management and followed to complete resolution (reports of any medical or surgical procedures and the resultant pathology must be provided to the Sponsor). The interpretation of the results by the three pathologists and their agreement or disagreement will be managed as described above in order to determine the final diagnosis for all endometrial biopsies (those scheduled during the study and "for cause" [for example, vaginal bleeding]).

The date of specimen collection will be entered in the eCRF. Details about the central pathology laboratory are provided in Section 10.1.

7.6.6 Vaginal Bleeding

If a subject reports vaginal bleeding during the study, an attempt will be made to determine the etiology. The possibility of a recent biopsy or other invasive procedure or vaginal atrophy as a cause for the bleeding should be considered. Visual inspection and gynecological examination will be performed. If no obvious reason can be identified and the subject has an intact uterus, a TVU will be performed to assess possible uterine pathology and the thickness of endometrium. In addition, the adnexa will be assessed.

If the endometrium is < 4 mm, an endometrial biopsy will be performed. If the biopsy yields an insufficient sample and bleeding persists, a hysteroscopy and guided biopsy will be performed. If the endometrium is ≥ 4 mm, a hysteroscopy and guided biopsy will be performed. The Investigator should assess the event of vaginal bleeding and its etiology for potential report as an AE. In cases, where the etiology is identified, the etiology should be reported as the AE term. When the etiology cannot be determined, the AE term should be vaginal bleeding. All drugs and procedures used for the diagnosis and/or treatment of vaginal bleeding should be captured in the eCRF.

A flowchart for the suggested process to assess vaginal bleeding in subjects with intact uterus is provided in Appendix 9.

7.6.7 Physical Examinations

The physical examination should be performed according to the normal practice of the clinical study site by the Investigator. This should include the examination of general appearance, skin, neck (including thyroid), eyes, ears, nose, throat, lungs, heart, abdomen, extremities, and body weight.

Information about all physical examinations must be included in the source documentation at the study site and be signed and dated by the Investigator or designee. Only new, abnormal findings in the physical examination should be captured in the

eCRF. Significant changes in the physical examination should be assessed by the Investigator or Sub-investigator and considered for potential reporting as an AE.

7.6.8 Vital Signs

Vital signs (BP, pulse rate, and oral temperature) will be measured by a qualified site staff member. Height will be measured in centimeters and weight in kilograms.

The BP and pulse rate will be measured after the subject has been in a sitting or recumbent position for ≥ 3 minutes. The BP and pulse rate will be measured by the Investigator or designee by using a blood pressure cuff of an appropriate size.

The Investigator or Sub-investigator will determine whether any abnormal changes from baseline (Visit 2) are clinically significant. Results of BP, oral temperature, pulse rate, height and weight will be entered into the eCRF. BMI will be automatically calculated in the eCRF.

7.6.9 Electrocardiograms/Electrocardiography

A standard 12-lead ECG will be performed at screening after the subject has been in a supine position for at least 5 minutes.

The Investigator or designee will be responsible for reviewing the ECG to assess whether it is normal or abnormal; abnormal ECG findings will be further divided into clinically significant and not clinically significant.

The ECGs will be retained as source documents and must be signed and dated by the Investigator or designee. Clinically significant findings observed at screening must be discussed with the Sponsor's medical monitor or designee to determine whether or not to enroll the subject in the study and must be recorded in the eCRF if enrolled. The date performed, ECG test result (normal or abnormal), and assessment of clinically significant findings will also be recorded in the eCRF.

7.6.10 Clinical Laboratory Tests

7.6.10.1 Laboratory Parameters

Safety laboratory tests are shown in Table 7.6-1 and the Schedule of Time and Events, Table 3.1-1.

Subjects will be in a seated or supine position during blood collection. At Visit 1, routine laboratory tests may not be fasting. Starting at Visit 2 patient should fast at least 8 hours prior to obtaining laboratory samples.

At Screening, a one-time follow-up blood draw is allowed for retest of abnormal values that could exclude the subject from study participation. If the retest is again abnormal, the subject should be excluded.

Table 7.6-1 Laboratory Tests

| Category | Evaluation Items |
|----------------------------|---|
| Hematology Tests | hematocrit, hemoglobin, platelet count, red blood cell (RBC) count, white blood cell (WBC) count with differential (eosinophil count, basophil count, neutrophil count, monocyte count, lymphocyte count), platelet count, mean corpuscular hemoglobin (MCH), mean corpuscular hemoglobin concentration (MCHC), mean corpuscular volume (MCV), RBC distribution width (RDW), mean platelet volume (MPV) |
| Blood Chemistry Tests | ALP, ALT, AST, total bilirubin, GGT, LDH, BUN, creatinine, uric acid, sodium (Na), potassium (K), chloride (Cl), calcium (Ca), glucose, total protein, |
| Lipids | Total cholesterol, Low-density lipoprotein (LDL) cholesterol, Very-low-density lipoprotein (VLDL) cholesterol, High-density lipoprotein (HDL) cholesterol, and Triglycerides |
| Coagulation | Thromboplastin time, Fibrinogen, Antithrombin III, Factor V Leiden (screening only), Protein-C, and Protein-S |
| Urinalysis for Qualitative | pH, specific gravity, color, bilirubin, glucose, ketones, nitrite, occult blood, protein, urobilinogen, and microscopic evaluation of sediment |

Abbreviations: ALT = alanine aminotransferase; AST = aspartate aminotransferase; ALP = alkaline phosphatase; GGT = gamma glutamyl transferase; LDH, lactate dehydrogenase; BUN, blood urea nitrogen.

The Investigator or Sub-investigator will assess whether any abnormal changes from baseline (Visit 2) are clinically significant. Clinically significant changes in laboratory parameters should be considered by the Investigator for reporting as adverse experiences as long as they reflect a change/worsening from baseline. The date of specimen collection will also be entered in the eCRF.

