10 SAFETY

Safety analyses will be conducted on the Safety Population. For all safety analyses, emphasis will be on characterizing the changes from baseline and flagging clinically relevant abnormal findings, if feasible. If a test or assessment is measured more than once prior to the first dose of study medication, the baseline measurement is the last non-missing value that is observed prior to the first dose of study medication.

To calculate 95% confidence intervals for differences in incidence proportions, FREQ procedure and RISKDIFF option will be used.

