2) Summary of TEAEs and Treatment-related AEs by System Organ Class and Preferred Term

For each treatment group, the number and percentage of subjects who experience TEAE (and Treatment-related AEs) will be counted by SOC and PT for assessments of short and long term safety. The difference in the percentage and its 95% CI will also be calculated. For assessment of short term safety, This analysis will be performed for specific TEAEs for assessment of short term safety, namely

- Breast-related TEAE
- Reproductive system-related TEAE
- Lipid-related TEAE
- Coagulation-related TEAE
- Chemistry-related TEAE

TEAEs and Treatment-related AEs at least 2% in any treatment groups will be analyzed in a similar way.

3) Summary of Serious TEAEs and TEAEs Leading to Withdrawal by System Organ Class and Preferred Term

For each treatment group, the number and percentage of subjects who experience serious TEAE and TEAE leading to withdrawal will be counted by SOC and PT for assessment of short term safety. The difference in the percentage and its 95% CI will also be calculated.

4) Summary of TEAEs and Treatment-related AEs by System Organ Class by Maximum Severity and Outcome

For each treatment group, the number and percentage of subjects who experience TEAE (and treatment-related AEs) will be counted by SOC and PT, and by maximum

severity and outcome for assessment of short term safety. The order of severity and outcome are shown in Table 6.

Table 6 Order of Priority for Counting Number of Subjects

Order of Priority	Severity	Outcome
1	Severe	Fatal
2	Moderate	Recovered/Resolved with sequelae
3	Mild	Not recovered/Not resolved
4		Recovering/Resolving
5		Recovered/Resolved
6		Unknown

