10.3 Laboratory Evaluations

Safety laboratory tests shown in Table 7 will be conducted at screening, randomization, Week 12, and early termination before Visit 5 (hereafter ET).

Table 7 Safety Laboratory Tests

Category	Evaluation Items
Hematology Tests	hematocrit, hemoglobin, platelet count, red blood cell (RBC) count, white blood cell (WBC) count with differential (eosinophil count, basophil count, neutrophil count, monocyte count, lymphocyte count), platelet count, mean corpuscular hemoglobin (MCH), mean corpuscular hemoglobin concentration (MCHC), mean corpuscular volume (MCV), RBC distribution width (RDW), mean platelet volume (MPV)
Blood Chemistry Tests	ALP, ALT, AST, total bilirubin, GGT, LDH, BUN, creatinine, uric acid, sodium (Na), potassium (K), chloride (Cl), calcium (Ca), glucose, total protein
Lipids	Total cholesterol, low-density lipoprotein (LDL) cholesterol, very-low-density lipoprotein (VLDL) cholesterol, high-density lipoprotein (HDL) cholesterol, and triglycerides
Coagulation	Thromboplastin time, fibrinogen, antithrombin III, , protein-C, and protein-S
Urinalysis for Quantitative	pH, specific gravity
Urinalysis for Qualitative	Color, bilirubin, glucose, ketones, nitrite, occult blood, protein, microscopic evaluation of sediment, and urobilinogen

ALT = alanine aminotransferase; AST = aspartate aminotransferase; ALP = alkaline phosphatase; GGT = gamma-glutamyl transferase; LDH, lactate dehydrogenase; BUN, blood urea nitrogen

The measurements on safety laboratory evaluations will be handled as follows:

- 1) For quantitative scale items, summary statistics of measurements taken at baseline, Week 12 will be calculated by treatment group. The change from baseline to Week 12 will be also calculated by treatment group.
- 2) For qualitative scale items, frequencies for each category at baseline, Week 12 will be counted by treatment group.
- 3) For all laboratory analytes in Appendix 3, proportion of subjects who meet the predefined limits at any timepoints will be calculated. Difference in the incidence proportion among treatments and its 95% CI will be calculated. This analysis will be performed using data until Visit 5. The analysis will be applied to data taken at the last timepoint before stopping dosing until Visit 5.

The factor V Leiden will not be summarized.

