Appendix 3 Pre-defined Limits of Change for Laboratory Test

Test Name (Unit)	Criteria
Hemoglobin (g/dL)	Decrease from baseline ≥ 1.5 g/dL
WBC Count ($10^3/\mu\text{L}$)	Decrease from baseline $\geq 50\%$ and value $< \text{LLN}$
	Increase from baseline $\geq 20\%$ and value $> \text{ULN}$
Neutrophil Count ($10^3/\mu\text{L}$)	Decrease from baseline $\geq 20\%$ and value $< \text{LLN}$
	Increase from baseline $\geq 20\%$ and value $> \text{ULN}$
Lymphocyte Count ($10^3/\mu\text{L}$)	Decrease from baseline $\geq 20\%$ and value $< \text{LLN}$
	Increase from baseline $\geq 20\%$ and value $> \text{ULN}$
Platelet Count ($10^3/\mu\text{L}$)	Decrease from baseline $\geq 25\%$ and value $< \text{LLN}$
	Increase from baseline $\geq 100\%$ and value $> \text{ULN}$
BUN (mg/dL)	Increase from baseline $\geq 50\%$ and value $> \text{ULN}$
Creatinine (mg/dL)	Increase from baseline ≥ 0.3 mg/dL
Total Bilirubin (mg/dL)	Increase from baseline $\geq 50\%$ and value $> \text{ULN}$
AST (U/L)	Value $> 3 \times \text{ULN}$
	Value $> 5 \times \text{ULN}$
	Value $> 10 \times \text{ULN}$
	Value $> 20 \times \text{ULN}$
ALT (U/L)	Value $> 3 \times \text{ULN}$
	Value $> 5 \times \text{ULN}$
	Value $> 10 \times \text{ULN}$
	Value $> 20 \times \text{ULN}$
AST (U/L) or ALT (U/L)	Value $> 3 \times \text{ULN}$
	Value $> 5 \times \text{ULN}$
	Value $> 10 \times \text{ULN}$
	Value $> 20 \times \text{ULN}$
AST (U/L) or ALT (U/L) + Total Bilirubin (mg/dL)	(AST $> 3 \times \text{ULN}$ or ALT $> 3 \times \text{ULN}$) + Total Bilirubin $> 2 \times \text{ULN}$ simultaneously
Alkaline Phosphatase (U/L)	Increase from baseline $\geq 50\%$ and value $> \text{ULN}$
Creatine Kinase (CK) (U/L)	Value $> 5 \times \text{ULN}$
Potassium (mmol/L)	Value $> \text{ULN}$ and $> \text{Baseline}$
	Value $< \text{LLN}$ and $< \text{Baseline}$
Sodium (mmol/L)	Value $> \text{ULN}$ and $> \text{Baseline}$
	Value $< \text{LLN}$ and $< \text{Baseline}$
Calcium (mg/dL)	Value $> \text{ULN}$ and $> \text{Baseline}$
	Value $< \text{LLN}$ and $< \text{Baseline}$

ALT = alanine aminotransferase; AST = aspartate aminotransferase; ALP = alkaline phosphatase; BUN, blood urea nitrogen; GGT = gamma-glutamyl transferase; LDH = lactate dehydrogenase; WBC = white blood cell

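### Coagulation and lipid values have no pre-defined limit in SAP Appendix 3, so marked changes in them get no between-arm proportion unless an investigator reports them as adverse events

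*Protocol*

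**What the plan says.** **Collection.** Protocol Table 7.6-1 (section 7.6.10.1) gives the coagulation panel as "Thromboplastin time, Fibrinogen, Antithrombin III, Factor V Leiden (screening only), Protein-C, and Protein-S". SAP Table 7 gives the lipids as "Total cholesterol, low-density lipoprotein (LDL) cholesterol, very-low-density lipoprotein (VLDL) cholesterol, high-density lipoprotein (HDL) cholesterol, and triglycerides". SAP 10.3 places safety laboratory tests at screening, randomization, Week 12 and early termination (ET) before Visit 5.

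**Analysis of measured values.** SAP 10.3 item 1 reads "For quantitative scale items, summary statistics of measurements taken at baseline, Week 12 will be calculated by treatment group", and adds the change to Week 12 by arm. It plans no between-arm difference and no CI. Item 3 reads "For all laboratory analytes in Appendix 3, proportion of subjects who meet the predefined limits at any timepoints will be calculated", followed by the difference between treatments with a 95% CI.

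**Limits.** "Appendix 3 Pre-defined Limits of Change for Laboratory Test" covers hematology, renal and liver tests, CK and electrolytes. For potassium, sodium and calcium the rule is a value above ULN and above baseline, or below LLN and below baseline.

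**Other routes.** SAP 10.1 item 2 plans a table for "Coagulation-related TEAE" and one for lipid-related TEAEs, each with the difference in percentage and its 95% CI. SAP 6.1 includes minimum and maximum among the summary statistics. Protocol 9.1 promises listings of all subject data. SAP section 10 puts the emphasis on changes from baseline and on "flagging clinically relevant abnormal findings, if feasible".

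**The concern.** The protocol treats clotting as a risk to be screened for: Exclusion 13 covers any thromboembolic or coagulation disorder and Exclusion 25 covers Factor V Leiden carriers. The SAP makes coagulation and lipids two of its five specific TEAE groups. Yet sodium and potassium get a count of women beyond a limit, with a difference and CI, while antithrombin III, protein C, protein S and the lipids do not. The SAP gives no reason.

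Primary Objective 2 is safety relative to placebo. If a minority of women had a marked change in one of these values, the laboratory tables would give neither the number affected per arm nor an estimate of the difference. The gap is in the SAP; the protocol's list of tests is not at fault.

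**Working it through.** **Step 1: match the analytes.** The coagulation row of Table 7.6-1 has six entries. Factor V Leiden is for screening only, so 6 − 1 = 5 are repeated on treatment. With five lipids, that makes 10. Appendix 3 has 15 distinct analytes: hemoglobin, WBC, neutrophils, lymphocytes, platelets, BUN, creatinine, total bilirubin, AST, ALT, ALP, CK, potassium, sodium and calcium. Overlap: 0 of 5 coagulation tests and 0 of 5 lipids.

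**Step 2: follow an early-termination sample.** SAP 6.3 assigns ET data to a visit by the windows in Table 1, where Week 12 is Day 72 to Day 99. An ET sample before Day 72 is therefore not a Week 12 value. Item 1 tabulates only baseline and Week 12, so for these ten analytes that sample enters no summary table. Item 3 counts limits met at any timepoint up to Visit 5, but does not cover these analytes. For bone markers, by contrast, SAP 9.2.10 adds a Week 12/ET analysis.

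**Step 3: what a count could add.** The plan has no figure to reproduce here. The only documented input is 300 per arm (SAP 4.3). The rest is assumed: a normal analyte with SD 1, reference limits at ±1.96 SD, baseline–Week 12 correlation ρ of 0.6 or 0.8, and a fraction q of the ospemifene arm shifted down by δ.

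- Mean difference = qδ. Its SE = √{[4(1 − ρ) + q(1 − q)δ²]/300}. The chance that its 95% CI excludes zero is about Φ(qδ/SE − 1.96).
- For q = 5%, δ = 3: qδ = 0.15 SD and q(1 − q)δ² = 0.4275.
  - ρ = 0.6: SE = √(2.0275/300) = 0.082, so Φ(−0.14) ≈ 0.45.
  - ρ = 0.8: SE = √(1.2275/300) = 0.064, so Φ(0.38) ≈ 0.65.
- Count below LLN and below baseline: about 2% of unaffected women meet it (2.2% at ρ = 0.6, 2.0% at ρ = 0.8, or 6–7 of 300). About 85% of women shifted by 3 SD meet it. At ρ = 0.6 the ospemifene proportion is 0.95 × 2.2% + 0.05 × 85% ≈ 6.3%, a difference of about 4 points.

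Chance that the 95% CI excludes zero, by simulation (4000 trials per setting; each range runs from ρ = 0.6 to ρ = 0.8):

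| Assumed pattern on ospemifene | CI for mean difference | CI for count difference |
|---|---|---|
| 5% fall 3 SD | 44–65% | 74–75% |
| 3% fall 3 SD | 20–31% | 38–42% |
| 5% fall 2 SD | 24–43% | 37–41% |
| All shift 0.2 SD | 79–97% | 16–18% |

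The count gains when few women change a lot. It gains nothing for a 2 SD fall at ρ = 0.8, and it loses clearly when everyone shifts a little. As planned, these analytes get neither interval.

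**The case against.** A reader might infer that the plan makes no between-arm comparison of coagulation or lipid safety, or that a marked change in a few women would simply be averaged away. The documents support neither reading. SAP 10.1 item 2 compares coagulation- and lipid-related TEAEs between arms with a 95% CI. The summary statistics include minimum and maximum, also for the change. In the scenario of 5% falling 3 SD, the median minimum change is about −4.5 SD on ospemifene against −2.5 on placebo (ρ = 0.6), or −4.1 against −1.8 (ρ = 0.8), so the extremes would be visible. All data are listed.

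Other points on that side also stand. Protocol 9.11.3 promises only summary statistics for laboratory data, so item 3 is an addition and there is no contradiction. Appendix 3 is a subset that also omits, for example, GGT, LDH, glucose and uric acid. The aim in SAP section 10 is qualified by feasibility. Symptomatic events become TEAEs without any laboratory judgement, and Protocol 7.6.11.7 says when a result counts as clinically significant. Nothing in the documents says that a signal would be confined to a minority of women.

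These points do not close the gap. An abnormal value without symptoms becomes a TEAE only through the investigator's judgement. No numeric limit is given for these tests, and the SAP does not list the terms that make up the two TEAE groups. A minimum describes one woman per arm and gives no number affected. Listings compare nothing. Feasibility is no obstacle, because the data and a usable rule already exist.

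**Conclusion.** The point holds in a limited form. All ten analytes (five coagulation tests, five lipids) are outside Appendix 3. Marked changes in their measured values therefore have no pre-defined limit and no between-arm proportion, and ET values before Day 72 enter no summary table for them. The omission follows from the documents alone and rests on no assumption.

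The size of the gain does rest on assumptions: 300 per arm, normal values, ±1.96 SD limits and correlation 0.6–0.8. It ranges from about 75% against 44–65% (5% of women falling 3 SD) to none (a 2 SD fall at correlation 0.8), and the count does worse under a uniform shift. The count should therefore stand beside a comparison of means and should not replace it. No co-primary endpoint is affected. This is an inexpensive improvement to the safety reporting and should be made.

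**What to change.** Before unblinding:

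1. Add thromboplastin time, fibrinogen, antithrombin III, protein C, protein S, total, LDL, VLDL and HDL cholesterol and triglycerides to SAP Appendix 3. Use the two-sided rule already applied to potassium, sodium and calcium, or limits that the sponsor justifies, with a stated direction of concern where only one matters.
2. State in SAP 10.3 item 3 that ET samples before Visit 5 count. Its closing sentence, on the last timepoint before dosing stops, could be read more narrowly.
3. Add a 95% CI for the between-arm difference in mean change for these analytes, because a uniform shift is better detected that way.
4. List the terms that make up the coagulation- and lipid-related TEAE groups.
5. Label the added rows descriptive.

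**Cost.** At most 10 × 2 = 20 rows and ten mean-change intervals, all from data already collected, with no new sample or procedure. With no drug effect, about 20 × 0.05 = 1 of the count intervals would exclude zero by chance. About 2% of unaffected women per arm would meet each one-sided limit, so a few cases in both arms are expected background.
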